### *Handling protocol deviations and violations, lost to follow up and withdrawal*

For each group the number of patients with protocol violation and deviation will be reported and specified with reasons. In case of withdrawal of consent and lost to follow-up, the number of patients will be reported, figure 2.

- In case of protocol violation, patient data will not be available for analyses and patients will be excluded from the trial.
- In case of protocol deviation patients will be included in the ITT analysis
  - o Not receiving the surgical treatment as assigned by randomisation, whether or not due to technical reasons → patients will be included in the ITT analysis according to the originally assigned study arm at baseline
  - o No endoscopy postoperatively → if a patient meets the 6 months follow up, but endoscopy could not be performed due to patients specific reasons (i.e. pregnancy), or the quality was insufficient to score endoscopic recurrence, MR or ultrasound to define recurrence will be accepted for the ITT analysis.
- In case of withdrawal of consent, patient data will not be available for analysis and patients will be excluded from the trial.
- Patients who are lost to follow up prior to the primary endpoint will be excluded from all outcome analyses. Baseline data will be reported.

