## STUDY METHODS

### Objectives

The aim of the SPICY study was to determine whether extended mesenteric resection results in reduced postoperative recurrence rates in CD patients undergoing ICR, compared to a mesenteric-sparing ICR. The primary outcome is the endoscopic recurrence rate at six months postoperatively, defined as a modified Rutgeerts score of  $\geq 2b$ , according to central reading.

The secondary outcomes are:

1. The degree of postoperative endoscopic recurrence (classified according to the modified Rutgeerts score), according to blinded central reading by two experts.
2. Perioperative data (i.e. operative time, per-operative blood loss, conversion rate)
3. Postoperative outcomes
  - Postoperative morbidity <30 days (length of hospital stay, anastomotic leakage and Clavien dindo score.
  - Histopathological data (length of resected colon, length of resected ileum, inflammation resection margins)
  - Postoperative medication (continuation Crohns' medication postoperatively, endoscopically guided start of Crohns' medication)

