## **STUDY POPULATION**

### **Sample size**

This study was powered to detect a clinically relevant difference of 25 per cent in endoscopic recurrence at 6 months between the two techniques: 60 per cent versus 35 per cent (a risk reduction of 45 per cent). Assuming a chi-square test for two independent proportions powered at 80 percent and a two-sided  $\alpha$ -level of 0.05, a total of 62 patients in each surgical arm are required, for a total enrolment of 124 patients. Allowing for a 10 percent dropout, the aim was to enrol 138 patients.[13]

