## STATISTICAL PRINCIPLES

### **Analyses methods**

All statistical tests will be two-sided and results will be presented with 95% confidence intervals. P-values of less than 0.05 will be considered statistically significant. Missing data in baseline characteristics or outcomes will be reported.

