### **Analysis populations**

Data analyses will be conducted according to the intention-to-treat (ITT) principle. All included patients will be analysed according to their originally assigned study arm at baseline.

Two additional analyses will be considered:

- Per protocol analysis:

In the case of > 5% protocol deviations, a per-protocol analysis will be performed for patients who received endoscopy with a central reading score. All patients with a protocol deviation will be excluded from this analysis.

- As treated analysis:

[figure not shown]
In the case >5% patients not receiving their intervention as indicated by randomisation, an additional 'as treated' analysis will be presented with patients analysed in the study arm of the received treatment.

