**Harms**

Serious Adverse Events (SAEs) are registered at the Central Committee on Research Involving Human Subjects (CCMO) and will be presented in the manuscript. All postoperative complications and needed re-interventions will be reported as secondary outcome parameter in postoperative morbidity.

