### **Challenges**

The main challenge of the SPICY study was conducting the study and ensuring adequate follow-up during the COVID pandemic. In the published protocol, the primary endpoint was defined as endoscopic recurrence after six months. ECCO guidelines recommend surveillance endoscopy between 6 months and 1 year after surgery. Therefore, endoscopies performed later, due to longer waiting lists, were accepted (maximum median of 1 year per group is accepted).

Another challenge in designing the SPICY study concerned defining the eligible population. For this study, external validity was considered more important than internal validity because there are too many confounding factors during the perioperative phase (i.e. surgical procedure, anastomotic configuration and type of anastomosis, radicality of resection, presence of a perianal fistula and use of postoperative medication for other reasons). Therefore, a more heterogeneous group representative of the target population undergoing ICR surgery was included.

Finally, all patients in whom a recurrence was assessed around 6 months postoperatively were included in the ITT analysis. The aim of this study was to analyse whether extended mesenterectomy lowers the risk of developing postoperative recurrence (objectified by endoscopy, MR or ultrasonography). In the context of external validity, we present all results from patients with completed follow-up (ITT analysis). The percentages and degree of endoscopic recurrences, according to central reading, is presented separately.

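### Patients lost before the six-month endpoint are dropped from every outcome analysis, which discards operative, histology and 30-day data already recorded and leaves a completer set called ITT with no missing-outcome check

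*SAP*

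**What the plan says.** - **The exclusion rule** (Handling protocol deviations and violations, lost to follow up and withdrawal): "Patients who are lost to follow up prior to the primary endpoint will be excluded from all outcome analyses". The next sentence keeps their baseline data and nothing else.
- **The stated principle** (Analysis populations): ITT, with "All included patients will be analysed according to their originally assigned study arm at baseline".
- **The set actually called ITT** (Challenges): "we present all results from patients with completed follow-up (ITT analysis").
- **Early outcomes** (Objectives): operating time, blood loss and conversion; resected lengths and margin inflammation; and "Postoperative morbidity <30 days (length of hospital stay, anastomotic leakage and Clavien dindo score". Table 4 lists the same items.
- **Complications** (Harms): "All postoperative complications and needed re-interventions will be reported as secondary outcome parameter in postoperative morbidity". SAEs are also to be presented.
- **Missing data** (Analyses methods): "Missing data in baseline characteristics or outcomes will be reported". Nothing further is specified.
- **Patients who reach six months without a usable endoscopy** (same section as the exclusion rule): "MR or ultrasound to define recurrence will be accepted for the ITT analysis". They stay in the analysis and are not affected by this point.
- **Planned loss** (Sample size): "Allowing for a 10 percent dropout, the aim was to enrol 138 patients".

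**The concern.** The rule ties every outcome, including those fixed on the day of surgery, to whether the patient later reaches the six-month endpoint. A patient lost at month 4 has a recorded operating time, blood loss, specimen and 30-day course, and all of it would leave Table 4. The operative and short-term safety comparison is then conditioned on an event after randomisation. If loss is related to the surgical course and differs by arm, that comparison is selected, and nothing is gained in exchange.

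The rule also cannot be applied together with the Harms section or with a plain reading of Analysis populations. Two analysts following different sections would produce different Table 4 denominators.

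For the primary endpoint, some patients will inevitably have no outcome. The problem there is that the completer set carries the ITT label and no planned analysis shows how far the losses could move the result.

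**Working it through.** **1. Which outcomes need six-month follow-up**

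| Outcome | Known by | Needs the six-month visit? |
|---|---|---|
| Operating time, blood loss, conversion | Surgery | No |
| Resected lengths, margin inflammation | Specimen | No |
| Hospital stay, leakage, Clavien-Dindo score | Day 30, as the SAP defines morbidity | No |
| Medication continued directly after surgery | Early postoperative period | No |
| Endoscopically guided medication; total on medication at six months | Endoscopy / six months | Yes |
| Recurrence (Tables 2 and 3) | Endoscopy, or MR/ultrasound | Yes |

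Only the last two rows justify an exclusion for loss before the primary endpoint.

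**2. Whether another section repairs the rule**

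None does. Analyses methods only reports missingness. The per-protocol and as-treated analyses are each triggered by a 5% threshold and deal with deviations and treatment received, not missing outcomes. MR or ultrasound helps only patients who meet the six-month follow-up.

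**3. The plan's own sample size**

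Inputs from Sample size: 60% versus 35%, two-sided alpha 0.05, power 80%, chi-square test. With pooled proportion 0.475 under the null:

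n = [1.960·√(2·0.475·0.525) + 0.842·√(0.60·0.40 + 0.35·0.65)]² / 0.25² = 61.4, so 62 per arm and 124 in total.

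124 / 0.90 = 137.8, so 138. The stated figures reproduce.

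**4. Size of the possible loss**

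138 − 124 = 14, or 7 per arm with equal losses. This is a ceiling, because withdrawals and protocol violations may use part of the allowance. At the ceiling, Table 4 falls from 69 to 62 per arm, and standard errors grow by √(69/62) = 1.055, about 5.5%.

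**5. Bounds for the primary endpoint**

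Assumptions: completers match the design as closely as whole patients allow, 37/62 sparing and 22/62 extended. The SAP does not say which arm has which rate; 60% for sparing follows from the superiority aim. The test is the chi-square without continuity correction.

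| Outcomes of the 7 lost per arm | Sparing | Extended | Difference (points) | p |
|---|---|---|---|---|
| Ignored (completers) | 37/62 | 22/62 | 24.2 | 0.007 |
| All extended recur, no sparing | 37/69 | 29/69 | 11.6 | 0.17 |
| All sparing recur, no extended | 44/69 | 22/69 | 31.9 | 0.0002 |
| All recur in both arms | 44/69 | 29/69 | 21.7 | 0.011 |
| None recur in either arm | 37/69 | 22/69 | 21.7 | 0.010 |
| 4 of 7 recur in both arms | 41/69 | 26/69 | 21.7 | 0.011 |

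**6. How many patterns reverse significance**

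With L lost per arm there are (L+1)² combinations of recurrence counts.

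| L | Patterns with p ≥ 0.05 | Largest p |
|---|---|---|
| 3 | 0 of 16 | 0.035 |
| 4 | 1 of 25 | 0.055 |
| 5 | 3 of 36 | 0.084 |
| 6 | 6 of 49 | 0.12 |
| 7 | 10 of 64 | 0.17 |

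At L = 7 the tipping pairs (sparing recurrences, minimum extended recurrences) are (0,4), (1,5), (2,6) and (3,7). Every one needs an excess of at least 4 in the extended arm.

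**7. How likely those patterns are**

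Weighting the L = 7 grid by binomial probabilities, the chance of p ≥ 0.05 is about 0.2% if the lost patients recur at 60% and 35%, and about 2.9% if they recur at 50% in both arms. These weights apply only if loss is unrelated to outcome within each arm.

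**The case against.** The primary-endpoint part should not be oversold. The patterns in the grid are not equally likely. With losses unrelated to outcome within arm, reversal has a chance of about 0.2% to 2.9% even at the ceiling, and none at 3 or fewer lost per arm. **This stands**, and it is why the figures are bounds and not expected bias. It does not cover informative loss, which is what a sensitivity analysis examines, and a weaker completer result would be more fragile.

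The CONSORT diagram and the n per arm in Table 2 would let a reader construct a best/worst-case table. **This stands in part**: the information would probably be there, but the analysis would not be prespecified.

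The ITT label is disclosed, since the exclusion is stated and Challenges describes patients with completed follow-up. The sentence in Analysis populations can be read as saying which arm patients count in, not who is counted. **This stands**: the label is the smallest part and changes no result.

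On Table 4, the authors may have meant the rule for recurrence outcomes only, the precision loss is modest, SAEs are presented separately, and nothing in the document shows that loss is related to surgery. Patients lost before surgery have no early data to restore. **These points limit the harm but do not remove it.** The wording says all outcome analyses, and SAE reporting does not return operative data, non-serious complications or leakage by arm to Table 4.

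**Conclusion.** The concern holds and should be fixed. Its core rests on the wording alone: the rule removes recorded operative, histology and 30-day data, conditions Table 4 on a later event, and contradicts the Harms section. At most 7 patients per arm are affected if the dropout allowance is met, equally by arm, and consists entirely of loss to follow-up.

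For the primary endpoint, the missing sensitivity analysis is a real but lesser gap. Under the same ceiling and completers at the design rates, the possible difference spans 11.6 to 31.9 points, but a change of conclusion requires strongly opposite recurrence among the lost patients in the two arms. The naming of the set is minor, and the conclusion does not depend on it.

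**What to change.** 1. **Handling section.** Replace the rule with wording such as: *Patients lost to follow-up before the primary endpoint are excluded only from the six-month outcomes (Tables 2 and 3, and the endoscopically guided and six-month medication rows of Table 4). They remain, by randomised arm, in all operative, histopathology, 30-day morbidity and harms analyses for which their data were recorded.*
2. **Analysis populations and Challenges.** Call the primary set *patients with completed follow-up (modified ITT)*. Because protocol violations and withdrawals of consent are also removed, list those exclusions in the definition.
3. **Outcomes.** Add one prespecified missing-outcome sensitivity analysis for the primary endpoint, such as a best/worst-case or tipping-point table by arm. Multiple imputation is optional.

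The cost is SAP wording and one extra table, with no added patients or data collection. Denominators will differ between rows, so n must be shown for each. Patients lost before surgery or before day 30 will still have absent or incomplete early data.

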### **Analysis populations**

Data analyses will be conducted according to the intention-to-treat (ITT) principle. All included patients will be analysed according to their originally assigned study arm at baseline.

Two additional analyses will be considered:

- Per protocol analysis:

In the case of > 5% protocol deviations, a per-protocol analysis will be performed for patients who received endoscopy with a central reading score. All patients with a protocol deviation will be excluded from this analysis.

- As treated analysis:

[figure not shown]
In the case >5% patients not receiving their intervention as indicated by randomisation, an additional 'as treated' analysis will be presented with patients analysed in the study arm of the received treatment.

### **Timing of final analyses**

The SPICY trial was considered a low-risk trial by the Medical Ethical Committee of the Amsterdam UMC. Therefore, no data safety monitoring board was set up and no interim analysis was planned.

The statistical analysis of the primary (endoscopic recurrence) and secondary outcomes as previously described, will be performed and presented in the initial manuscript when every patient has reached six months follow-up, data entry and cleaning has been completed.

Figure 2. CONSORT FLOW diagram SPICY, intention to analysis for primary outcome parameter

Table 1 Baseline characteristics			
n (%) , median (IQR)	Extended mesenterectomy (n=)	Mesenteric sparing (n=)	p-value
Age at surgery, years			
Sex (male)			
Disease duration at surgery, months			
Smoker			
Active			
Ex-smoker			
BMI (kg/m  )			
Age at onset			
A1, ≤16 years			
A2, 16-40 years			
A3, ≥40 years			
Behaviour of disease			
B1, inflammatory			
B2, stricturing			
B3, penetrating			
Perianal disease			
Location of disease			
L1, terminal ileum			
L3, ileocolic			
Crohns' medication <12weeks before operation			
No medication			
Thiopurines			
Steroids			
Biologicals			
Small molecules			
BMI: body mass index			

Table 2. Primary outcome			
n %, median (IQR)	Extended mesenterectomy (n=)	Mesenteric sparing (n=)	P value
Endoscopic recurrence rate,			
Time between surgery and endoscopy, months			

Table 3. Secondary outcomes			
Outcomes central reading			
n (%)	Extended mesenterectomy (n=)	Mesenteric sparing (n=)	P value
Endoscopic recurrence rate, according to the modified Rutgeerts score			

*\*Degree of recurrence, according to tmodified Rutgeerts score will be presented in a bar chart, figure 3*

Table 4. Secondary outcomes			
Perioperative outcomes			
n %, median (IQR)	Extended mesenterectomy (n=)	Mesenteric sparing (n=)	P value
Per-operative data			
Operating time, hours			
Operative blood loss, cc			
Conversion rate			
Postoperative morbidity <30 days			
Length of hospital stay, days			
Anastomotic leakage			
Clavien Dindo score			
Histopathological data			
Radical resection			
Both sides no inflammation			
Distal inflammation			
Proximal inflammation			
Inflammation on both sides			
Length of resected ileum, cm			
Length of resected colon, cm			
Postoperative medication			
Continuation of Crohn medication immediately after surgery			
No medication			
Thiopurines			
Biologicals			
Small molecules (JAK)			
Endoscopically guided start of postoperative Crohn medication			
No medication			
Thiopurines			
Biologicals			
Small molecules (JAK)			
Total on medication after 6 months			

**Harms**

Serious Adverse Events (SAEs) are registered at the Central Committee on Research Involving Human Subjects (CCMO) and will be presented in the manuscript. All postoperative complications and needed re-interventions will be reported as secondary outcome parameter in postoperative morbidity.

**MANUSCRIPT AND AUTHORSHIP**

The SPICY study group will share the results irrespective of the outcomes. The manuscript will be submitted on behalf of the SPICY study group, the coordinating study team will be mentioned as co-authors. The coordinating investigator and principal investigator will be respectively first and senior author on the manuscript. Members of the SPICY study group will be mentioned in alphabetical order.

## **DISCUSSION**

This SAP describes the intended analyses of data collected throughout the study upon completion of follow-up of the respective outcome. By publishing the SAP, we aim to increase the transparency of data analyses.

### **Challenges**

The main challenge of the SPICY study was conducting the study and ensuring adequate follow-up during the COVID pandemic. In the published protocol, the primary endpoint was defined as endoscopic recurrence after six months. ECCO guidelines recommend surveillance endoscopy between 6 months and 1 year after surgery. Therefore, endoscopies performed later, due to longer waiting lists, were accepted (maximum median of 1 year per group is accepted).

Another challenge in designing the SPICY study concerned defining the eligible population. For this study, external validity was considered more important than internal validity because there are too many confounding factors during the perioperative phase (i.e. surgical procedure, anastomotic configuration and type of anastomosis, radicality of resection, presence of a perianal fistula and use of postoperative medication for other reasons). Therefore, a more heterogeneous group representative of the target population undergoing ICR surgery was included.

Finally, all patients in whom a recurrence was assessed around 6 months postoperatively were included in the ITT analysis. The aim of this study was to analyse whether extended mesenterectomy lowers the risk of developing postoperative recurrence (objectified by endoscopy, MR or ultrasonography). In the context of external validity, we present all results from patients with completed follow-up (ITT analysis). The percentages and degree of endoscopic recurrences, according to central reading, is presented separately.

## **Funding**

The SPICY trial is an investigator study, with funding from TKI-LSH with no influence on protocol writing, data collection and interpretation or access to data.

## **Ethics approval and consent to participate**

This study has been approved by the Amsterdam UMC Medical Ethical Committee. The protocol is registered by the Dutch Central Committee on Research Involving Human Subjects (NL61632.018.18). For all other participating centres, approval of the local ethical committee and/or board of directors was obtained. This study has been performed in accordance with the principles of Good Clinical Practice.

## **Availability of data and materials**

The data that support the findings of this study are available, upon reasonable request.

## **Competing interests**

None to declare.

## **List of abbreviations**

BMI – Body mass index; CCMO - Central Committee on Research Involving Human Subjects; CD – Crohn's disease; ECCO – European Crohns and Colitis Organisation; ICR – ileocolic resection; ITT – intention to treat; IQR – interquartile range; SAE - Serious Adverse Events; SAP – statistical analysis plan

